3.5 Explanatory Variables

These include demographic and clinical variables (such as age, gender, history of prior exposure, age at first exposure, duration of opioid therapy, use of concomitant medications, etc.) in order to identify possible risk factors for development of opioid tolerance during PICU therapy, and to generate hypotheses for future studies. In addition, since some opioid drugs are highly lipophilic (e.g. fentanyl) and others are not (e.g. morphine), we will calculate BMI and ideal body weight to evaluate the impact of increasing obesity on opioid tolerance.

3.6 Patient Eligibility

3.6.1 Inclusion Criteria

Critically ill children admitted to the PICU are eligible for enrollment if they are:

- between 37 weeks post-conceptional age and less than 18 years; AND
- receiving ventilatory assistance through an endotracheal tube or a tracheostomy; AND
- receiving fentanyl or morphine infusion for analgesia or sedation.

3.6.2 Exclusion Criteria

Children are ineligible to be enrolled as study subjects if ANY of the following is true or anticipated:

- are premature and have not reached the post-conceptional age of 37 weeks, OR
- have a history of drug abuse or alcohol dependence, OR
- for patients less than 3 months old, if the mother has a history of drug abuse during this pregnancy, OR
- are on ECMO or are likely to be placed on ECMO support within 24 hours after PICU admission, OR
- are receiving continuous infusions (of any drugs) for nerve blocks, plexus blocks, or epidural anesthesia, OR
- are receiving opioid therapy via patient-controlled analgesia (PCA) pumps, OR
- were receiving regularly scheduled opioid therapy for more than one week before admission to the PICU, OR
- previously enrolled in this study, OR
- lack of commitment to aggressive intensive care therapies.

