3.7 Inclusion of Women and Minorities

The gender, ethnic and racial composition of patients enrolled in all CPC-CRN studies is a function of the characteristics of patient populations at each Clinical Center selected by the National Institute for Child Health and Human Development (NICHD) to participate in the network. During this study, the Data Coordinating Center (DCC) will monitor patient accrual by race, ethnicity, and gender. If necessary, additional recruitment efforts will be made at specific centers to ensure that the aggregate patient sample contains appropriate gender and minority subsets.

4 Data Management

Research data will be collected at the time of enrollment and daily data collection will continue until the last dose of opioids, or a total of 14 days after enrollment, or the patient's death or PICU discharge, whichever occurs first.

This protocol includes a detailed list of data elements to be collected, and if data elements are added or subtracted from this, a protocol amendment will be produced. However, specific choice sets for these data may be amended without being considered a change to this protocol. The choice sets that are listed in the protocol are intended to help the reader completely understand the intent of the data element and to assist implementation of the electronic data collection system by the CPCCRN DCC.

Data will be entered into an electronic data collection system to be designed and implemented by the CPCCRN DCC. The Study Coordinator may choose to print hard copy forms to use as worksheets. If used, the paper worksheets should be retained at the clinical center in a locked file cabinet within a locked office until the study is complete and all CPCCRN publications associated with MOTIF have been accomplished.

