4.1 Definitions

- **Analgesia:** the reduction or absence of the sense of pain without loss of consciousness, as reported by the patient, or judged clinically from the patients behavior or physiological responses
- **Sedation:** a pharmacologically produced depressed level of consciousness associated with reduced anxiety, stress, and excitement

- First study day: the period from the time that the initial dose of opioid is received in the PICU up to 23:59 hours on that day
- **Subsequent study days:** each calendar day starting at midnight (00:00 hours) and ending at 23:59 hours after the completion of the first study day (as defined above) during which the enrolled subject is an inpatient in the PICU
- **Ventilated day:** PICU day during any part of which the child requires mechanical ventilation support greater than chronic baseline requirements (out of the hospital), provided by endotracheal tube, tracheostomy, laryngeal or face mask
- **Invasive procedure:** Any procedure that breaks the skin barrier or mucous membrane barrier or involves the placement of a medical device (catheter, probe, electrode, drain, prosthetic, or anything else) into a body orifice or body cavity, other than momentary suctioning of the nose, mouth, endotracheal tube, or tracheostomy tube.
- **Opioid tolerance:** the need for increasing doses of opioid drugs in order to maintain the same pharmacological effects as those seen at the initiation of therapy. For the purposes of this study, opioid tolerance is clinically defined as a doubling of the total daily opioid dose (including infusions and boluses) as compared to the total daily opioid dose required during the first 24 hours of opioid therapy, in order to maintain adequate analgesia and sedation
- **Regularly scheduled opioids:** the subject receives opioid drugs daily, given at regularly scheduled intervals. In response to specific symptoms or signs, if the subject has received more than one opioid dose per day, on more than three days during the past week, or a total of more than six opioid doses in the past one week, then they will be considered equivalent to those receiving regularly scheduled opioids.
- **Chronic opioid treatment:** if the subject has received scheduled regular opioids (as defined above) for more than one week, they will be classified as receiving chronic opioid treatment.

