4.4 Study Exit Data Elements

The following data will be recorded when the patient exits the study:

- 1. Study day of exit from study (1 to 14)
- 2. Time of exit from study (hh:mm)
- 3. Reason for exiting study:
 - (a) Reached end of study day 14
 - (b) Opioid therapy was discontinued
 - (c) Patient died
 - (d) Patient discharged from PICU
- 4. If reason for study exit was PICU discharge:
 - (a) Was patient on lorazepam at the time of PICU discharge? (Yes or No)
 - (b) Was patient on methadone at the time of PICU discharge? (Yes or No)
 - (c) Was patient on buprenorphine at the time of PICU discharge (Yes or No)
 - (d) Was patient on clonidine (for prevention or treatment of opioid withdrawal) at the time of PICU discharge (Yes or No)

5 Data Analysis

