5.1 Analysis of Primary Endpoint

The primary endpoint for the MOTIF Study is the incidence of opioid tolerance among PICU patients receiving morphine or fentanyl infusions for analgesia and sedation. For the purposes of this study, opioid tolerance is defined by a doubling of the total daily opioid dose from the initiation of opioid therapy (0-24 hours) in the PICU. Tolerance can develop at any time during opioid therapy; therefore, as would be the case for an intention-to-treat analysis in a clinical trial, subjects who die or are discharged from the PICU will be included in the denominator for this endpoint, irrespective of number of days in PICU prior to death or discharge. We will examine the incidence of this endpoint 7 days and 14 days after initiation of morphine or fentanyl infusion therapy, in order to help determine appropriate parameters for future clinical trials. Rates of the primary endpoint will be summarized as proportions achieving tolerance by 7 days and by 14 days after opioid therapy initiation, together with appropriate confidence intervals.

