5.3 Explanatory Variables and Additional Analyses

These include demographic and clinical variables (such as age, gender, history of prior exposure, age at first exposure, duration of opioid therapy, use of concomitant medications, etc.) in order to identify possible risk factors for development of opioid tolerance during PICU therapy, and to generate hypotheses for future studies. In addition, since some opioid drugs are highly lipophilic (e.g. fentanyl) and others are not (e.g. morphine), we will calculate BMI and ideal body weight to evaluate the impact of increasing obesity on opioid tolerance.

In exploratory analyses, we will also assess rates of the primary and secondary endpoints according to other explanatory study variables. Factors examined in these analyses will include age, gender, history of prior exposure, age at first exposure, duration of opioid therapy, use of concomitant medications, and BMI. For continuous factors, categories will be defined using clinically appropriate cut-points, or quartiles of the observed data when such cut-points do not exist or are equivocal. Chi-squared tests or exact analogues will be used to compare proportions achieving the endpoint between subgroups. Logistic regression models will be used to assess factors that are independently predictive of tolerance, starting with candidate factors showing at least a weak statistical trend toward unadjusted association with the endpoint.

This study will be collecting information on other outcomes, for example, clinical status at PICU discharge and other clinical variables. The general strategy for analyses of other outcomes collected in this study will follow that specified for the primary and secondary study endpoints. Other binary or categorical outcomes such as PICU and hospital survival will be compared using chi-square tests or exact analogues. For other continuous outcome variables, summary statistics and box-plots will be used to investigate their distributions. Where indicated in order to ensure satisfaction of assumptions, we will either use transformations or non-parametric statistics.

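### An opioid doubling that first occurs after redirection to comfort care is scored as tolerance, and nothing collected after enrolment identifies these children

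*Protocol*

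**What the plan says.** **Eligibility.** Protocol section 3.6.2 (repeated in 1.6.2) opens with "Children are ineligible to be enrolled as study subjects if ANY of the following is true or anticipated" and lists "lack of commitment to aggressive intensive care therapies" among the exclusions. The criterion therefore covers a foreseen as well as a present lack of commitment, but it is a condition of enrolment and is not revisited.

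**Follow-up.** The opening of section 4 (Data Management) states that "daily data collection will continue until the last dose of opioids, or a total of 14 days after enrollment, or the patient's death or PICU"; the last item in that list is leaving the unit, and the earliest event applies. Under "Reason for exiting study", section 4.4 offers four options: end of day 14, opioids stopped, death and PICU discharge. None of the 26 daily elements in section 4.3 records withdrawal of life-sustaining treatment, a move to comfort care, or why a dose was raised.

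**Endpoint.** Section 5.1 states that "opioid tolerance is defined by a doubling of the total daily opioid dose from the initiation of opioid therapy (0-24 hours) in the PICU", with no condition on the purpose of the increase, and that "subjects who die or are discharged from the PICU will be included in the denominator for this endpoint". Section 4.1 is narrower. It describes tolerance as needing more drug to keep the effect seen at the start of therapy, and it ties the doubling to a purpose: "in order to maintain adequate analgesia and sedation".

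**Survival.** Section 5.3 says "Other binary or categorical outcomes such as PICU and hospital survival will be compared using chi-square tests or exact analogues". It does not name the groups to be compared. It adds that tolerance-related parameters may serve as predictors in selected analyses.

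**The concern.** The protocol places children without commitment to intensive care outside its target population, yet a child who reaches that state after enrolment stays in the scored data. Once the goal of care has changed, the intended drug effect has changed too. A higher dose is then no longer evidence that more drug is needed for the same effect. Section 5.1 counts the doubling regardless, and the purpose qualifier in section 4.1 cannot be applied because no collected element bears on it. The definition and the data set do not match.

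Two results are exposed. The incidence of tolerance gains some false cases. These also fall mostly among children who die, so any analysis that sets tolerance against survival can pick up an association that the scoring rule produced. The dose endpoints in section 5.2 (average daily dose, peak rate, cumulative dose) take in the same end-of-life dosing.

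**Working it through.** **1. The plan's own precision.** Half-width of a 95% interval = 1.96 × √(p(1−p)/450).
- p = 0.25 (the lowest outcome rate section 5.4 assumes): 4.0 points.
- p = 0.30: 4.2 points.
- p = 0.50: 4.6 points.

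This reproduces the 4–5% in section 5.4.

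**2. Inputs for the size of the problem.** Only N = 450 comes from the protocol. The rest are assumptions:
- true tolerance t = 30%, unrelated to death;
- PICU mortality m = 4–8%;
- share of deaths preceded by redirection c = 50–70%;
- share of otherwise non-tolerant children in that group whose dose first doubles after redirection q = 30–60%.

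**3. False tolerance cases** = 450 × (1−t) × m × c × q.
- Low: 450 × 0.70 × 0.04 × 0.50 × 0.30 = 1.9 children; 1.9/450 = 0.4 points.
- High: 450 × 0.70 × 0.08 × 0.70 × 0.60 = 10.6 children; 10.6/450 = 2.4 points.

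**4. Apparent link with death.** Scored tolerance among deaths = t + (1−t) × c × q; among survivors it is t.
- Low: 0.30 + 0.70 × 0.15 = 0.405. Odds ratio = (0.405/0.595)/(0.30/0.70) = 1.6.
- High: 0.30 + 0.70 × 0.42 = 0.594. Odds ratio = (0.594/0.406)/(0.30/0.70) = 3.4.

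Mortality cancels out of this ratio.

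**5. Wider assumptions** (t 25–50%, m 3–10%, c 30–70%, q 25–75%). These give about 0.5 to 18 false cases, 0.1 to 3.9 points, and odds ratios of 1.2 to 5.4. A middle case (t 25%, m 6%, c 50%, q 50%) gives 450 × 0.75 × 0.06 × 0.25 = 5 cases, 1.1 points. Scored tolerance among deaths is then 0.25 + 0.75 × 0.25 = 0.4375, an odds ratio of 2.3. Even the largest shift, 3.9 points at t = 25%, is just under the 4.0-point half-width there.

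**6. The opposing effect.** Children who die early have less time in which to double, so their genuine tolerance rate may be below 30%. In the low case of step 4 the two effects cancel when that rate, x, satisfies x + (1−x) × 0.15 = 0.30, so x = 0.15/0.85 = 17.6%. In the high case even x = 0 leaves 42% of deaths scored as tolerant against 30% of survivors, so cancellation is impossible if q is as assumed. The protocol does not say where between these cases the study would fall.

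**The case against.** Much of the case on the other side stands.

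- **Foreseen cases are already excluded.** The criterion covers an anticipated lack of commitment, so only redirection not foreseen at entry is left. That may lower the share c.
- **The wording of 4.1 helps.** On its terms a purely end-of-life escalation need not count. But section 5.1 omits the qualifier and no data element lets an analyst apply it.
- **A brief escalation may not double a daily total.** Suppose a baseline rate r for 24 hours, no change until noon, escalation at noon and death at 15:00. Doubling then needs 12r + 3kr ≥ 48r, so k ≥ 12. A child already above baseline, or redirected for a full day or more, needs far less. The assumed q of 30–60% is therefore uncertain and drives the result.
- **Exit data allow a partial check.** Doublings first seen in the last day or two before death could be discounted using the exit time and the daily doses. That cannot show whether or when care was redirected, and it would also remove genuine late tolerance.
- **Not every limitation is comfort care.** A child with one therapy limited may remain ventilated on an infusion, become genuinely tolerant, and survive. Stopping the scoring at any limitation would bias incidence downward.

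A reader might infer that the plan builds in a false association between tolerance and death. The documents do not support that. No such test is specified: survival is listed among other outcomes without named groups, and tolerance parameters are only optional predictors. Shorter time at risk also pulls the other way, so the net size and direction are not established.

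**Conclusion.** The point holds in a limited form. Commitment to intensive care is checked only at enrolment, later redirection to comfort care leaves no trace in the data, and section 5.1 scores a doubling that first occurs afterwards as tolerance although the meaning given in section 4.1 is not met.

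On the main assumptions the primary incidence rises by 0.4 to 2.4 points (about 2 to 11 of 450 children), which is inside the stated precision. It would be wrong to infer that the incidence estimate is unusable or that the sample size must change. The larger exposure is in any exploratory analysis relating tolerance to death: an odds ratio of about 1.6 to 3.4 with no true link, before the opposing effect of shorter follow-up. Every rate behind these figures is assumed; the protocol gives none for mortality, redirection or late doubling.

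**What to change.** Add one element to sections 4.3/4.4: the date and time of any withdrawal of life-sustaining treatment or redirection to comfort care. Do not trigger it on every partial limitation. Keep the child in the section 5.1 denominator. Report incidence, the dose endpoints and any comparison of tolerance with survival with doses after that time not counted, at least as a prespecified sensitivity analysis beside the bare-doubling result.

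This concerns data capture and scoring only; care and N = 450 are unchanged. The opening of section 4 requires a protocol amendment for an added data element, so an analysis plan alone cannot supply the field. The cost is that amendment, one form field, the last day or two of dose data for a few children in the restricted analysis, and a small risk of missing genuine late tolerance.

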3.7 Inclusion of Women and Minorities

The gender, ethnic and racial composition of patients enrolled in all CPC-CRN studies is a function of the characteristics of patient populations at each Clinical Center selected by the National Institute for Child Health and Human Development (NICHD) to participate in the network. During this study, the Data Coordinating Center (DCC) will monitor patient accrual by race, ethnicity, and gender. If necessary, additional recruitment efforts will be made at specific centers to ensure that the aggregate patient sample contains appropriate gender and minority subsets.

4 Data Management

Research data will be collected at the time of enrollment and daily data collection will continue until the last dose of opioids, or a total of 14 days after enrollment, or the patient's death or PICU discharge, whichever occurs first.

This protocol includes a detailed list of data elements to be collected, and if data elements are added or subtracted from this, a protocol amendment will be produced. However, specific choice sets for these data may be amended without being considered a change to this protocol. The choice sets that are listed in the protocol are intended to help the reader completely understand the intent of the data element and to assist implementation of the electronic data collection system by the CPCCRN DCC.

Data will be entered into an electronic data collection system to be designed and implemented by the CPCCRN DCC. The Study Coordinator may choose to print hard copy forms to use as worksheets. If used, the paper worksheets should be retained at the clinical center in a locked file cabinet within a locked office until the study is complete and all CPCCRN publications associated with MOTIF have been accomplished.

4.1 Definitions

- **Analgesia:** the reduction or absence of the sense of pain without loss of consciousness, as reported by the patient, or judged clinically from the patients behavior or physiological responses
- **Sedation:** a pharmacologically produced depressed level of consciousness associated with reduced anxiety, stress, and excitement

- First study day: the period from the time that the initial dose of opioid is received in the PICU up to 23:59 hours on that day
- **Subsequent study days:** each calendar day starting at midnight (00:00 hours) and ending at 23:59 hours after the completion of the first study day (as defined above) during which the enrolled subject is an inpatient in the PICU
- **Ventilated day:** PICU day during any part of which the child requires mechanical ventilation support greater than chronic baseline requirements (out of the hospital), provided by endotracheal tube, tracheostomy, laryngeal or face mask
- **Invasive procedure:** Any procedure that breaks the skin barrier or mucous membrane barrier or involves the placement of a medical device (catheter, probe, electrode, drain, prosthetic, or anything else) into a body orifice or body cavity, other than momentary suctioning of the nose, mouth, endotracheal tube, or tracheostomy tube.
- **Opioid tolerance:** the need for increasing doses of opioid drugs in order to maintain the same pharmacological effects as those seen at the initiation of therapy. For the purposes of this study, opioid tolerance is clinically defined as a doubling of the total daily opioid dose (including infusions and boluses) as compared to the total daily opioid dose required during the first 24 hours of opioid therapy, in order to maintain adequate analgesia and sedation
- **Regularly scheduled opioids:** the subject receives opioid drugs daily, given at regularly scheduled intervals. In response to specific symptoms or signs, if the subject has received more than one opioid dose per day, on more than three days during the past week, or a total of more than six opioid doses in the past one week, then they will be considered equivalent to those receiving regularly scheduled opioids.
- **Chronic opioid treatment:** if the subject has received scheduled regular opioids (as defined above) for more than one week, they will be classified as receiving chronic opioid treatment.

4.2 Study Entry and Day One Data Elements

The following data elements will be obtained and recorded when a patient is enrolled into the study:

- 1. Study Code ID
- 2. Clinical Center ID
- 3. Date of Enrollment
- 4. Date and Time of Admission to PICU
- 5. Gender
- 6. Race
 - American Indian or Alaska Native A person having origins in any of the original peoples of North and South America, including Central America, and who maintains tribal affiliation or community attachment.
 - Asian A person having origins in any of the original peoples of the Far East, Southeast Asia, or the Indian subcontinent, including, for example, Cambodia, China, India, Japan, Korea, Malaysia, Pakistan, the Philippine Islands, Thailand, and Vietnam.
 - **Black or African American** A person having origins in any of the black racial groups of Africa.
 - Native Hawaiian or Other Pacific Islander A person having origins in any of the original peoples of Hawaii, Guam, Samoa, or other Pacific Islands.
 - White A person having origins in any of the original peoples of Europe, the Middle East, or North Africa.
 - Other (provide text) Should provide text description.

Stated as Unknown Explicitly stated as unknown.

- 7. Ethnicity
 - Hispanic or Latino
 - Not Hispanic or Latino
 - Stated as Unknown
- 8. Date of Birth
- 9. Height (cm)
- 10. Weight (kg)

- 11. Admission Pediatric Risk of Mortality III (PRISM III) Score (Based on first 12 hours of PICU admission)
- 12. History of previous PICU admission (Yes or No)?
- 13. History of NICU admission (Yes or No)? If yes, duration in days.
- 14. History of surgical operation in previous hospitalizations (Yes or No)?
- 15. Primary Diagnostic Category (Select One)
 - Asthma (reactive airway disease)
 - Cancer
 - Cardiac arrest w/in 24 hours (closed chest massage)
 - Chromosomal abnormality
 - Diabetes
 - Drug overdose (e.g. ingestion, toxicity)
 - Gastroesophageal reflux
 - Cardiovascular disease acquired
 - Cardiovascular disease congenital
 - HIV infection
 - Hypoxic-ischemic encephalopathy of recent onset (acute, not static)
 - Medical device malfunction
 - Meningitis
 - Pneumonia / bronchiolitis
 - Seizures (includes complications of seizure therapy)
 - Sepsis
 - Shock
 - Suicide attempt (includes intentional drug overdose)
 - Transplant
 - Trauma
 - Other Diagnosis
- 16. Secondary Diagnostic Category (Select One)
 - Asthma (reactive airway disease)

- \bullet Cancer
- Cardiac arrest w/in 24 hours (closed chest massage)
- Chromosomal abnormality
- Diabetes
- Drug overdose (e.g. ingestion, toxicity)
- Gastroesophageal reflux
- Cardiovascular disease acquired
- Cardiovascular disease congenital
- HIV infection
- Hypoxic-ischemic encephalopathy of recent onset (acute, not static)
- Medical device malfunction
- Meningitis
- Pneumonia / bronchiolitis
- Seizures (includes complications of seizure therapy)
- Sepsis
- Shock
- Suicide attempt (includes intentional drug overdose)
- Transplant
- Trauma
- Other Diagnosis
- 17. Chronic Diagnoses (Select Multiple)
 - Bronchopulmonary dysplasia (BPD)
 - Cancer
 - Cerebral palsy
 - Chromosomal abnormality
 - Congenital heart disease
 - Diabetes
 - HIV infection
 - Hydrocephalus
 - Intraventricular hemorrhage (from perinatal period)
 - Mental retardation

- Meningomyelocele / spina bifida
- Short gut syndrome
- Static encephalopathy
- Transplant
- Other Diagnosis
- 18. Postoperative Surgical Status (Select one)
 - Not postoperative
 - Postoperative
 - Cardiac surgery
 - Neurosurgery
 - Transplant surgery
 - Trauma surgery
 - Other surgery
- 19. Date and time of start of mechanical ventilation via endotracheal tube or tracheostomy during current hospital admission
- 20. Date and time of first morphine or fentanyl dose in the PICU this is defined as Time 0 for the baseline opioid dose
- 21. Total amount of morphine or fentanyl (mg/kg) given before midnight on the first study day (total amounts of drug infusions plus additional boluses of morphine or fentanyl)
- 22. Total amount of midazolam or lorazepam (mg/kg) given before midnight on the first study day (total amounts of drug infusions plus additional boluses of midazolam or lorazepam.
- 23. Other sedative (Table 1 on the following page) or analgesic (Table 2 on page 23) agents used during the first study day. If drug combinations are used, record all components of the drug combination.

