2.3 Epidemiology of Opioid Tolerance in PICU Patients

Clinical studies of neonates born to heroin-addicted or methadone-maintained mothers were previously extrapolated to the introgenic opioid tolerance caused by prolonged opioid therapy.^{5, 9} Iatrogenic opioid tolerance in young children was first reported from a retrospective chart review in neonates undergoing ECMO,⁵⁶ with 5-fold increases in the fentanyl infusion rate and increases in plasma fentanyl concentrations over 8 days of therapy.^{56, 57} Opioid withdrawal symptoms occurred following a total fentanyl dose of >1.6mg/kg or fentanyl infusions for longer than 5 days.^{56, 57} Subsequent reports^{58–61} suggested that opioid withdrawal occurs in 57% of PICU patients⁷ and in >60% of PICUs, ⁶² despite careful attention to opioid weaning.^{63–65} Increased complications^{66, 67} and prolonged hospital stays occurred among critically ill children with opioid tolerance.^{4, 68} Despite a deeper understanding of the mechanisms underlying opioid tolerance and dependence,⁶⁹ and the availability of novel therapies,^{70–72} none of these advances have been applied to the care of critically ill children. This is mainly because the current prevalence of opioid tolerance in PICU patients remains unknown, and associated risk factors contributing to tolerance in PICU patients have not been described.

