3.3 Primary Endpoint

The primary endpoint for the MOTIF Study is the incidence of opioid tolerance among PICU patients receiving morphine or fentanyl infusions for analgesia and sedation. For the purposes of this study, opioid tolerance is defined by a doubling of the total daily opioid dose from the initiation of opioid therapy (0-24 hours) in the PICU.

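### For children who arrive in the PICU already on opioids, the protocol gives two baselines and two clocks for tolerance, and no data element identifies these children

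*Protocol*

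**What the plan says.** - **Eligibility.** Protocol 1.6.2 and 3.6.2 exclude children who "were receiving regularly scheduled opioid therapy for more than one week before admission to the PICU". A shorter course does not exclude.
- **Time 0.** Section 4.2, item 20: "Date and time of first morphine or fentanyl dose in the PICU this is defined as Time 0 for the baseline opioid dose".
- **Primary endpoint.** Sections 1.3, 3.3 and 5.1: "opioid tolerance is defined by a doubling of the total daily opioid dose from the initiation of opioid therapy (0-24 hours) in the PICU".
- **Definition of tolerance.** Section 4.1 describes a need for more drug "in order to maintain the same pharmacological effects as those seen at the initiation of therapy". It makes this operational as a doubling "as compared to the total daily opioid dose required during the first 24 hours of opioid therapy". The PICU is not mentioned in that definition.
- **Clock.** Section 5.1 gives the 7- and 14-day horizons once from the start of infusion therapy and once from the start of opioid therapy. Neither is tied to the PICU.
- **Risk factors.** Section 5.3: "Factors examined in these analyses will include age, gender, history of prior exposure, age at first exposure, duration of opioid therapy".
- **Data collected.** The nearest entry items in 4.2 are previous PICU admission, NICU admission and surgery in an earlier hospital stay (items 12-14). Neither 4.2 nor 4.3 asks for the start, duration or dose of opioids given before this PICU admission. Section 4 makes any added element a protocol amendment.

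**The concern.** The primary endpoint is a ratio, so it depends on its denominator. For a child whose opioids start in the PICU, all the wordings agree. For a child who arrives after several days of opioids, 4.1 read literally takes the denominator from before admission, while 1.3, 3.3, 5.1 and item 20 take it from the first PICU day. The 7- and 14-day horizons shift in the same way.

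Two things are at stake. The first is what the reported incidence means: doubling since therapy began, or further doubling after PICU admission. The second is Specific Aim 2. Prior exposure is a planned factor, but the form cannot separate a child six days into opioid therapy on arrival from one who has never had an opioid. An analysis plan can choose between two definitions later. It cannot recover data that were never collected.

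**Working it through.** **1. The plan's own figure.** The 95% half-width is 1.96 × √(p(1−p)/450).
- p = 0.25: 1.96 × √(0.1875/450) = 4.0 points.
- p = 0.50: 1.96 × √(0.25/450) = 4.6 points.

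The precision of 4-5% in 5.4 therefore reproduces for rates of 25% to 75%. The present point does not affect it.

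**2. One child, two baselines.** The rule is peak daily dose / baseline daily dose ≥ 2. Take an illustrative child who started at 2 units/day and arrives in the PICU at 4.

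| PICU peak | Ratio to PICU baseline (4) | Ratio to true start (2) |
|---|---|---|
| 4 | 1.0, not tolerant | 2.0, tolerant |
| 7.9 | 1.98, not tolerant | 3.95, tolerant |
| 8 | 2.0, tolerant | 4.0, tolerant |

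The two readings disagree unless the dose doubles again after admission.

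**3. One child, two clocks.** Suppose the child arrives after 6 days of opioids. Counted from true initiation, the 7- and 14-day horizons fall 1 and 8 days after the first PICU dose. Counted from the first PICU dose, they fall 13 and 20 days after true initiation.

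**4. Effect on the incidence.** The documents do not give the share of pre-exposed children, so the following is a range under assumptions. Let
- a = share of enrolled children whose dose had already doubled on arrival (assumed);
- π = PICU doubling rate in the others, set at 25%, the minimum outcome rate in 5.4;
- r = PICU doubling rate in those already doubled (assumed between 0 and π).

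Incidence on the PICU baseline = (1−a)π + a·r. Incidence since true initiation = (1−a)π + a. The gap is a(1−r).

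| a | Children of 450 | Gap if r = 25% | Gap if r = 0 |
|---|---|---|---|
| 1.25% (5% pre-exposed, a quarter of them doubled) | about 6 | 0.9 points | 1.25 points |
| 5% (10% pre-exposed, half doubled) | about 23 | 3.75 points | 5.0 points |
| 10% (20% pre-exposed, half doubled) | 45 | 7.5 points | 10.0 points |

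This ignores the 7- and 14-day cut-offs. It also ignores children whose dose had risen but not doubled on arrival. For example, a 1.5-fold rise before and a 1.5-fold rise after admission make 2.25-fold overall, scored as 1.5.

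**5. Against the PICU endpoint itself.** The PICU incidence differs from π by a(π−r): 0 if r = π, and at most 0.10 × 0.25 = 2.5 points in this range. That is a change in case mix. The children are scored correctly for doubling within the PICU.

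**The case against.** The strongest reply is that the PICU baseline is a deliberate choice. It is written into the endpoint three times, matches item 20 and the first study day in 4.1, and fits the stated interest in tolerance during PICU therapy. This stands. For that endpoint the children are not misclassified, and only the 4.1 definition and the 5.1 clock are out of step. A pre-PICU baseline would have its own weakness: a dose rise at intubation would count, although 4.1 requires more drug for the same effect.

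A reader might infer more than the documents support:

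- *That every child tolerant on arrival is scored non-tolerant.* This holds only if the dose does not double again in the PICU.
- *That the permitted week covers a known period of steep escalation.* Section 2.3 cites a report "with 5-fold increases in the fentanyl infusion rate and increases in plasma fentanyl concentrations over 8 days of therapy", which at constant growth would mean doubling in 8 × ln 2/ln 5 = 3.4 days. That report is a retrospective review of neonates on ECMO, a group excluded here, and it concerns infusion rate, not total daily dose. It cannot size the effect in this cohort.
- *That prior exposure will look protective.* If children escalate in the PICU at the same rate whatever went before (r = π), prior exposure looks null. A protective appearance needs r < π, and nothing in the protocol settles that.
- *That the reported incidence is biased low overall.* Item 21 totals the first day only to midnight. If that total served as the baseline, a constant infusion begun 12 hours before midnight would give 24/12 = 2.0 with no escalation. That is a separate matter, but it pushes the other way, so the net direction is open.

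None of this answers the missing data. Item 19 dates the start of ventilation in the current hospital admission, but it says nothing about opioids.

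**Conclusion.** The point holds in a limited form. The definition in 4.1 and the horizons in 5.1 do not match the PICU-anchored endpoint for children who arrive on opioids, and the form cannot identify those children. As a result, the planned prior-exposure analysis must rest on past PICU or NICU admission or earlier surgery.

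The size cannot be computed from the documents. Relative to incidence since true initiation, the gap could be under 1 point (about 6 of 450 children already doubled on arrival) or 7.5 to 10 points (45 of 450), against a stated precision of 4-5%. These figures rest on assumed shares and a 25% doubling rate in the other children. Against an endpoint of doubling within the PICU, no bias is shown. The calculation for 450 children is unaffected. The change should be made before enrolment, because the missing information is not in the planned study data.

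**What to change.** 1. Reconcile 4.1 with 1.3, 3.3 and 5.1, so that the comparator and the 7- and 14-day clocks both run expressly from the first morphine or fentanyl dose in the PICU.
2. Add to the entry form in 4.2 the date and time opioid therapy began in this illness, and whether an opioid infusion was running on arrival in the PICU.
3. Keep all 450 children in the primary PICU-baseline incidence. Also report it separately for children whose opioids began in the PICU and for those arriving on opioids, labelling the latter *further doubling after PICU admission*. Use this variable in the prior-exposure analysis in 5.3.

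The cost is a protocol amendment, one or two chart-abstracted items per child, and wider intervals within strata. If 20% arrive on opioids, the PICU-started stratum has 360 children and its interval is √(450/360) = 1.12 times as wide, or about 4.5 points at p = 0.25. The other stratum, with 90 children, would have a half-width of 1.96 × √(0.1875/90) = 8.9 points at the same rate, so it is descriptive only. Restricting the primary estimate to PICU-started children is not needed and would narrow a population the protocol keeps broad on purpose.
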